4.2.2 Missing data algorithms for efficacy analyses

These descriptions focus on the missing data procedures themselves and do not specifically account for dealing with intercurrent events, which is addressed in their respective sections.

4.2.2.1 MI – MCMC / Monotone Regression

In many cases, missing efficacy data due to study treatment discontinuation should be dependent on the observed efficacy scores, but independent of unobserved data. This would be consistent with a missing at random (MAR) pattern of missingness. To investigate the efficacy results under the assumption of data being MAR, a multiple imputation method will be applied.

Binary endpoint

For a binary endpoint (eg, HiSCR₅₀), the procedure is as follows:

1. Create a data set, one for each treatment group of participants with observed values and those needing estimation by multiple imputation. For the imputation step, a distinction is made between non-monotone missing values (ie, intermittent missing values between completed assessments) and monotone missing values (ie, where all participants data are missing after a given time point).
 - a. For the intermittent missing values, the missing values in each data set will be filled in using the MCMC method with multiple chain, monotone missing data imputing pattern, and non-informative prior for all parameters. Unless specified differently, the first 200 iterations will not be used (the “Burn-in” option). A total of 100 sets of imputations will be performed. The seed used for these imputations will be 762 and all other multiple imputation procedures described in this SAP will use this same seed as well. The resulting 100 imputed data sets will have a monotone missing pattern and will be imputed using a method for monotone missingness. Note that a separate imputation procedure must be invoked in SAS for each treatment group as the seed cannot be set for by groups beyond the first when using a by statement in PROC MI.
 - b. For monotone missing data, monotone regression will be used to impute missing data. A separate regression model is estimated for each variable with missing values (ie, measurement at each time point). Based on the resulting model, a new regression model is then drawn and is used to impute the missing values for the variable. Since the data set has a monotone missing data pattern, the process is repeated sequentially for variables with missing values. This procedure will be based on the 100 imputed datasets generated from the MCMC procedure and will be performed by imputation. The SAS® PROC MI procedure will be used for the imputation.

In both cases, Hurley Stage at Baseline, Baseline antibiotic use, and value of the variable of interest at Baseline and at each post-Baseline visit (prior to the time point of interest) will be included in the imputation model. The post- Baseline values will need to be specified in chronological order in the imputation model so that SAS® PROC MI imputes variables from left to right (eg, the Week 2 value will be first imputed using regression based on the Baseline value, and then Week 4 value will be imputed using regression based on Baseline and Week 2 values, etc). The resulting data sets for each treatment arm will be combined into one complete data set based on each of the 100 imputations.

Note: The imputation model based on the MCMC method will only allow joint multivariate normal variables. Therefore, Hurley Stage at Baseline and Baseline antibiotic use will be re-coded as indicator variables. For Baseline antibiotic use, this will simply be 0 for Baseline antibiotic non-users and 1 for Baseline antibiotic users. For Hurley Stage at Baseline, this will be 0 for Hurley Stage II participants and 1 for Hurley Stage III participants. In order to

achieve model convergence, Baseline antibiotic use may be dropped from the model. If convergence is still not obtained, then Hurley Stage at Baseline may also be dropped from the model. Additionally, if a variable is dropped in order to allow convergence for one model in a study, that variable does not have to be dropped from other models in the study if the model converges without dropping the variable. In other words, model convergence should be evaluated for each efficacy variable independently.

Note: The imputation of each lesion type (inflammatory nodule, abscess, draining tunnel, etc) will be performed separately. The 100 data sets obtained for each type will be merged by imputation number and subject number.

2. For each complete imputed data set, the dichotomous responder variable (eg, HiSCR 0 or 1) will be computed. Each complete imputed data set will then be analyzed based on the logistic regression model.

Note: For derivation of HiSCR response, the AN, inflammatory nodule, abscess, and draining tunnel (fistula/sinus tract) counts at Week 16 in the imputed data sets will be compared directly to the observed Baseline counts to determine response. If values outside of the pre-defined range of values for lesion count (<0) are imputed, they will be cut off as appropriate after the multiple imputation procedure but before deriving the responder variable. For example, an imputed draining tunnel (fistula/sinus tract) count of -1 would be changed to 0 before deriving the HiSCR responder variable. Additional ranges for values for secondary and other endpoints are defined in Table 4-2.

Note: Standard rounding rules will also be applied to the imputed values of endpoints that can only take integer values (eg, abscess count). For example, if a study participant has an abscess count imputed as 2.4, this imputed value would be rounded down to 2. This rounding step is performed after the multiple imputation but before deriving the responder variable.

Table 4-2: Imputation allowable ranges by variable

Variable	Minimum Value	Maximum Value	Integer Values Only
Lesion count ^a	0	--	Yes
DLQI total score	0	30	Yes
hs-CRP	LLOQ/2	--	No
HSSDD item score	0	10	No
HSSQ item score	0	10	Yes
HiSQOL symptom status score	0	16	Yes
HiSQOL psychosocial impact score	0	20	Yes
HiSQOL impact on physical activities score	0	32	Yes
EQ-5D-3L VAS	0	100	Yes

Table 4–2: Imputation allowable ranges by variable

Variable	Minimum Value	Maximum Value	Integer Values Only
WPAI dimension scores	0	100	No for variables: “Percent work time missed due to problem” and “Percent overall work impairment due to problem”. Yes for variables: “Percent impairment while working due to problem” and “Percent activity impairment due to problem”. These two variables can only take values that are multiples of 10.

^aLesion counts will be imputed separately for each lesion type (abscesses, draining tunnels [fistulas/sinus tracts], inflammatory nodules, non-draining tunnels [fistulas/sinus tracts], non-inflammatory nodules, HS scars). The imputed lesion counts will be used to derive the endpoints that are dependent on the lesion count data (eg, HisCR₅₀).

3. Estimates of the adjusted responder rate for each treatment group and the associated SE are obtained from the logistic regression of each of the 100 imputed data sets. These estimates will be combined for overall inference using Rubin’s rules, which account for the uncertainty associated with the imputed values (Rubin, 1987), and the combined estimates and SEs will be used to construct 95% CIs using the logit scale. This will be done using SAS PROC MIANALYZE. The combined estimates and 95% CIs on the logit scale will be back-transformed using the inverse logit link function to obtain the adjusted responder rates (%) and associated 95% CIs.

Note: The (unadjusted) proportion of responders will be calculated at each time point by treatment group from the imputed datasets using SAS PROC FREQ. These results will also be combined into an overall inference using SAS PROC MIANALYZE.

Some key points to consider relative to the calculation of the odds ratios and corresponding confidence intervals are noted below:

As the estimates of the odds ratios from the logistic regression models in Step 3 follow a log-normal distribution, a log transformation is needed to normalize these 100 odds ratio estimates. That is because the procedures for combining results from multiple imputed datasets assume that the statistics estimated from each imputed dataset are normally distributed. Therefore, the log of the odds ratio estimates from the logistic regression model are used when combining into a single inference (Step 3). Additionally, the SE for the odds ratios are transformed as follows:

$$SE = \frac{\log(UCL) - \log(LCL)}{2Z_{\alpha/2}}$$

Where UCL and LCL are the upper and lower confidence limit, respectively, for the CI of the odds ratio from the logistic regression model, and $Z_{\alpha/2}$ is the relevant critical value from the standard normal distribution (2.24 for a 97.5% CI). The estimates of the log odds ratio for Bimekizumab relative to placebo and the corresponding upper and lower CLs will be provided. The odds ratio will be then estimated by exponentiating the estimate of the log odds ratio. The odds ratio and the confidence limits of the odds ratio will be estimated as follows:

$$OR = \exp(\text{Log odds ratio estimate})$$

$$LCL = OR * \exp(-SE * Z_{\alpha/2})$$

$$UCL = OR * \exp(SE * Z_{\alpha/2})$$

Where OR is the back-transformed estimate of the odds ratio just described, SE is the SE of the log odds ratio and $Z_{\alpha/2}$ is the relevant critical value from the standard normal distribution (2.24 for a 97.5% CI). These calculations will be done such that odds ratios and corresponding CIs are calculated for the odds ratio of bimekizumab vs. placebo.

Note: If one dose regimen is tested at the 0.05 significance level as determined in Section 4.5, then the confidence interval will be 95% instead of 97.5% for that dose with a corresponding $Z_{\alpha/2}$ of 1.96.

In addition to calculating the odds ratio, associated CIs, and p-values for the pairwise comparisons of bimekizumab and placebo, the estimated proportion of responders (ie, estimated responder rate) and the difference in the proportion of responders between each bimekizumab treatment group and placebo will be estimated, and 2-sided 95% CIs will be created for each difference. The creation of the estimates of the differences will be completed for each bimekizumab treatment group using the process detailed below:

1. Use the logistic regression model to calculate:

Least squares mean estimates of the log odds of bimekizumab (G_B) and placebo (G_P), as well as their corresponding standard errors (S_B and S_P , respectively).

Standard error of the least squares mean estimate of the log odds ratio (S_R)

2. Compute estimates for predicted proportions using the following transformations:

$$P_B = \exp(G_B) / (1 + \exp(G_B))$$

$$P_P = \exp(G_P) / (1 + \exp(G_P))$$

The difference in proportions is then given by:

$$D = P_B - P_P$$

3. Estimate the standard error of D by:

$$S_D = \sqrt{[P_B^2(1-P_B)^2S_B^2 + P_P^2(1-P_P)^2S_P^2 + P_B(1-P_B)P_P(1-P_P)S_R^2 - P_B(1-P_B)P_P(1-P_P)(S_B^2 + S_P^2)]}$$

The MCMC method for multiple imputation, as previously outlined, will be used to account for missing values. The calculation steps described above will be based on the results provided from the logistic regression model of the multiple imputed datasets. An estimate for the difference in proportions, D, and corresponding standard error, SD, will be computed for each of these datasets. The results from these analyses will be combined into a single estimate of the difference in predicted proportion of response and a 2-sided 95% CI interval using SAS PROC MIANALYZE.

Note that this procedure indicates that the imputation model will be applied for each treatment group separately in PROC MI, which will be the default method. However, in the event there are computational challenges with the imputation model (eg, due to a standard deviation of 0 for responses of a given imputation), it is acceptable to modify the imputation model to include treatment as a variable in the model rather than running a separate model for each treatment group. It should be noted that doing so assumes that treatment does not interact with any of the other variables in the imputation model.

Continuous endpoint

For continuous endpoints (eg, Change from Baseline in DLQI total score at Week 16), the MI method will be applied as follows:

1. The MCMC/monotone regression method described above in Step 1 for binary endpoints will be performed.
2. Based on the multiply imputed data sets obtained for the given variable, the change from Baseline will be derived for each of the 100 complete imputed data sets based on the observed Baseline value and the observed/imputed post-Baseline values. Note that if the value itself is being summarized, no additional derivation is needed.
3. If a statistical model is being used for the analysis of the variable, then that will be performed for each imputation in this step. If no statistical model is being used, then simple descriptive statistics will be calculated.
4. For data excluding hs-CRP, the following rules apply. The results of the 100 imputed data sets (based on the statistical model or descriptive statistics) are combined with means and standard errors calculated using Rubin's rules (via PROC MIANALYZE). Note that for the calculation of other descriptive statistics such as the median, min, and max, Rubin's rules do not apply. MI estimates will be computed by simply averaging the estimates from the multiple repetitions of the imputation algorithm. Thus, for median, Q1, Q3, minimum and maximum, the following approach will apply:
 - The data will be summarized by treatment, visit, and imputation, and the summary statistics will be computed.
 - Results will be summarized by taking the mean value of each summary statistic at each visit across all imputations.
 - The number of decimal places will remain the same as the original for display purposes (ie, if the mean was presented to 1 decimal place, then the mean of the means will also be presented to 1 decimal place).

For hs-CRP only, the following rules apply. The hs-CRP data will be presented using the geometric mean, 95% CI for the geometric mean, median, Q1, Q3, minimum and maximum. The change from Baseline will be expressed as the ratio to Baseline in the summaries. The following approach will be applied:

- Following the MI procedure, the ratio to Baseline will be calculated for any of the imputed values
- The natural logarithm of the absolute values and of the ratios to Baseline will be calculated

- The logged values will be summarized (using PROC MEANS) by treatment, visit and imputation
- The datasets will be combined using PROC MIANALYZE in order to get the mean and 95% CI estimates from the absolute values and ratios to Baseline (based on logged data) across imputations
- The estimates of the mean and 95% CI will be back-transformed to obtain the geometric mean and 95% CI on the original scale
- For the median, Q1, Q3, minimum and maximum the procedure outlined above for the other endpoints will be followed

If the imputation model cannot converge, LOCF will be used.

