2.4 Determination of sample size

A total of 490 study participants will be randomly assigned in a 2:2:2:1 ratio (stratified by Hurley Stage and current antibiotic use) to the following treatment arms:

- Bimekizumab 320mg Q2W during Initial Treatment Period (Weeks 0-16) and Maintenance Treatment (Weeks 16-48) Period, N=140
- Bimekizumab 320mg Q2W during Initial Treatment Period (Weeks 0-16), and Bimekizumab 320mg Q4W during Maintenance Treatment Period (Weeks 16-48), N=140
- Bimekizumab 320mg Q4W during Initial Treatment (Weeks 0-16) and Maintenance Treatment Periods (Weeks 16-48), N=140
- Placebo during Initial Treatment Period (Weeks 0-16), and Bimekizumab 320mg Q2W during Maintenance Treatment Period (Weeks 16-48), N=70

The analysis of the primary efficacy endpoint and secondary efficacy endpoints are based on a comparison of bimekizumab versus placebo at Week 16, with alpha adjustment strategy as indicated in Section 4.5.

The power to detect a statistically significant difference for each of the endpoints are shown in Table 2-1. Notably, with a 2-sided significance level of 0.025, the sample size of 140:70 provides 73% power for detecting at least a difference of 1.5 (bimekizumab Q4W vs placebo) for the Worst Skin Pain change from Baseline (CFB) endpoint.

Given the high level of power for each of the primary and key secondary endpoints at the 0.025 significance level for the Q2W comparison (power ≥ 0.89), and per the alpha spending strategy, there is a high likelihood that the Q4W comparison of Worst Skin Pain CFB vs placebo will be allowed to be tested against the 0.05 level of significance. The power for this latter test is 81%. The sample size is thus ultimately driven by the Worst Skin Pain CFB endpoint. Furthermore, the randomization ratio of 2:2:2:1 has been chosen to provide study participants with a high probability (6/7 ~ 86%) of being randomized to active study drug.

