After randomization for this study was complete, an additional endpoint to assess Worst Skin Pain response was included in the sequential testing procedure. This additional endpoint is based on the threshold for clinically meaningful change and is defined as at least a 3 point decrease from Baseline in HSSDD weekly worst skin pain score at Week 16 among study participants with a score of ≥ 3 at Baseline. Note that the power calculations reported in Table 2-1 for this endpoint are based on the sample size that was initially driven by the Worst Pain CFB endpoint as described above. With a 2-sided significance level of 0.025, the sample size of 104:52 in the subset of participants reporting Baseline HSSDD worst skin pain score at or beyond the threshold for clinically meaningful change (ie, Baseline HSSDD ≥ 3) provides 53% power for

detecting a statistically significant difference between bimekizumab Q4W and placebo in the proportion of Worst Pain responders.

Note that the power at the 0.025 level of significance associated with this endpoint for the comparison between bimekizumab Q2W and placebo is 95%. The Q4W comparison of Worst Skin Pain response vs placebo against the 0.05 level of significance is therefore likely, and the power at this significance level is 65%. Given the strength of the power for the bimekizumab Q2W arm vs placebo across endpoints, it is considered acceptable to have a relatively low power for this final endpoint in the testing sequence for the bimekizumab Q4W treatment arm vs placebo.

Table 2-1: Power calculation assumptions and methods

Endpoint	Power $\alpha = 0.025$, 2-sided		Assumptions		
	Q2W	Q4W	Week 16 Bimekizumab Q2W N=280 ^a	Week 16 Bimekizumab Q4W N=140	Week 16 Placebo N=70
HiSCR ₅₀	0.99	0.90	Proportion responders=0.60	Proportion responders=0.50	Proportion responders=0.25
HiSCR ₇₅	0.99	0.98	Proportion responders=0.45	Proportion responders=0.35	Proportion responders=0.10
DLQI	0.99	0.96	Mean CFB=-5.4; SD=6.8	Mean CFB=-4.8; SD=6.8	Mean CFB=-0.8; SD=6.6
Worst Skin Pain CFB ^b	0.89	0.73	Mean CFB=-2.2; SD=3.2	Mean CFB=-2.0; SD=3.2	Mean CFB=-0.5; SD=3.7
Worst Skin Pain Response ^c	0.95	0.53	Proportion responders=0.53	Proportion responders=0.43	Proportion responders=0.23

CFB=change from Baseline; Q2W=every 2 weeks; Q4W=every 4 weeks; SD=standard deviation

Note: Estimates for HS0003 are based on Week 12 data from the HS0001 study.

^a Pooled Q2W at Week 16 from Q2W/Q2W and Q2W/Q4W arms

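### The primary imputation handles each lesion count alone on a raw normal scale, so the link between counts that HiSCR needs is set by seed handling; hs-CRP is also imputed unlogged

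*SAP*

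**What the plan says.** SAP section 4.2.2.1 sets the imputation for the primary endpoint and most other efficacy endpoints.

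- **Separate runs.** "The imputation of each lesion type (inflammatory nodule, abscess, draining tunnel, etc) will be performed separately". The results are merged afterwards by imputation and participant number. The predictors are Hurley Stage, Baseline antibiotic use and the same variable's own earlier values; no other lesion type enters.
- **Scale.** The MCMC step for intermittent gaps is described as multivariate normal, and the monotone step is ordinary regression. No transformation is mentioned, and the SAP's own examples of imputed values are -1 and 2.4.
- **Range and rounding.** For values below 0, "they will be cut off as appropriate after the multiple imputation procedure but before deriving the responder variable". Counts are also rounded to integers before response is derived.
- **Seed.** The seed is 762, and "all other multiple imputation procedures described in this SAP will use this same seed as well". Section 4.2.2.2 nevertheless uses seeds 853 to 952 for the reference-based analysis.
- **hs-CRP.** Imputation comes first, with a minimum of LLOQ/2 (Table 4-2). Only then: "The natural logarithm of the absolute values and of the ratios to Baseline will be calculated".

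Section 8.2.1 defines HiSCR50 from three counts together: AN count down by at least half, with no rise in abscesses and no rise in draining tunnels.

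**The concern.** HiSCR depends on how the three counts move together and on whether a zero stays zero. The specified model protects neither.

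A participant with no draining tunnels at Baseline whose normal draw rounds to 1 becomes a nonresponder, whatever the nodules do. Separate runs estimate no association between lesion types, so whatever association the imputed values show comes from the random-number stream. If the seed is reset in each call and the same visits are missing for all three types, the draws are nearly the same number used three times. If the seeds differ, the draws are unrelated.

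The same imputations feed HiSCR50, HiSCR75, the other HiSCR endpoints and IHS4. For hs-CRP, the plan summarises by geometric mean but imputes as if the values were normal.

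**Working it through.** **1. The plan's own figure.** "Proportion responders=0.50" for Q4W and 0.25 for placebo (Table 2-1), with 140 and 70 participants at two-sided 0.025 (z = 2.2414).

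Pooled rate = (0.25×70 + 0.50×140)/210 = 0.4167. SE0 = √[0.4167×0.5833×(1/70 + 1/140)] = 0.0722. SE1 = √[0.25×0.75/70 + 0.50×0.50/140] = 0.0668. Power = Φ[(0.25 - 2.2414×0.0722)/0.0668] = Φ(1.32) = 0.907; Table 2-1 states 0.90. It reproduces, but it says nothing about the imputation. The SAP gives no lesion distribution, no share of zeros and no missing rate, so the rest rests on assumed inputs.

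**2. Simulation inputs (assumed).** Negative-binomial counts with Baseline means of 12 nodules, 2.5 abscesses and 3.5 draining tunnels; AN count at least 5; correlation 0.4 between types; correlation 0.6-0.9 between visits; monotone missingness completely at random; 40,000 per arm. Each type was imputed by sequential normal regression on its own history, floored and rounded.

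**3. Link between types.** Residual correlation was about 0.3 in the data, 0.91-0.94 with separate runs and one seed, and 0.00-0.02 with separate runs and different seeds.

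**4. Zeros.** Among participants with no draining tunnels at Baseline, an increase was imputed in 55-63% against a true 27-48%. Zero abscess counts were imputed in 36% against a true 50%.

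**5. HiSCR50 among participants with imputed data, base scenario (%).**

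| | True | Separate, raw, one seed (SAP) | Separate, raw, different seeds | Joint, raw | Joint, log(1+count) |
|---|---|---|---|---|---|
| Placebo | 30.0 | 33.6 | 13.1 | 19.0 | 27.3 |
| Q4W | 54.7 | 52.6 | 36.3 | 40.8 | 51.6 |
| Difference | 24.7 | 19.0 | 23.2 | 21.8 | 24.3 |

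Over all scenarios the SAP method erred by +2 to +5 points on placebo and 0 to -3 on Q4W. Different seeds erred by -12 to -18.

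**6. Other assumed counts.** With 19-37% zero tunnels at Baseline and true rates of 60% (bimekizumab) and 25% (placebo), shared draws gave 51-53% and about 25%, and independent draws gave 37-42% and 15-16%. The tunnel increase from zero was 38% imputed against 8% true. A third simulation, also on assumed skewed counts, gave a single-seed 54-56% against a true 57-62% on bimekizumab, and 27-31% against 25-27% on placebo. Taken together, the single-seed error is about 0 to -9 points on bimekizumab and 0 to +5 on placebo.

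**7. Whole arm.** Shift = error × fraction imputed. At 10%: -9 × 0.10 = -0.9 point. At 15%: +5 × 0.15 = +0.75, and at the far corner -9 × 0.15 = -1.35. In the simulations of step 2, power for Q4W against placebo fell by 0 to 5 points; the largest loss was 0.774 to 0.726 at 15% missing.

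**8. hs-CRP (assumed lognormal, true geometric mean about 5.0, log-SD 0.8 or 1.2).** Raw-scale imputation, floored at LLOQ/2 and then logged:

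- LLOQ 0.1: 3.26 against 5.05 (-35%) and 2.60 against 5.00 (-48%)
- LLOQ 0.3: 3.93 against 5.01 (-22%) and 3.72 against 4.97 (-25%)
- LLOQ 1.0: 4.53 against 5.00 (-9%) and 5.04 against 5.06 (about 0)

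Between 13% and 30% of draws were floored. Imputation on the log scale gave 4.94-5.04. The third simulation gave 2.8-3.6 against 5.0 at LLOQ 0.1-0.2 (-28% to -44%).

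**The case against.** Several counter-arguments stand in part.

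- **Exposure is limited.** Rescue antibiotics and discontinuation for an AE or lack of efficacy are already nonresponse (section 4.2.1.1), so the model touches only the remaining gaps. This stands, and is why the arm-level effect is small.
- **Other analyses avoid the model.** Nonresponse imputation (8.2.3.1), observed cases (8.2.3.5) and the worst-case scenario in 4.2.2.3 do not use it, and sections 8.4.1.1 and 8.4.2.1 display observed beside imputed data. This also stands. The treatment-policy, tipping-point and reference-based analyses, however, also impute the counts by normal-model PROC MI and would not reveal the problem.
- **Near-identical draws are conditional.** They need a per-call seed reset and the same missing pattern. The SAP also lets covariates be dropped model by model, which can break the match. This stands; it also means the association between lesion types is not fixed by the plan.
- **hs-CRP lies outside the testing hierarchy** and outside the nominal tests in section 8.5. Correct.

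A reader might infer that the plan cuts imputed response on bimekizumab from 60% to about 40%. That result belongs to independent draws, whereas the plan fixes one seed. A reader might also infer that the bias is always larger on bimekizumab. The simulations disagree on that: in one set placebo moved more, and upward.

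**Conclusion.** The concern holds as a weakness of method with a modest effect on the trial. The specified imputation misstates the joint distribution behind HiSCR. Under assumed skewed counts, the single-seed method shifts HiSCR50 among participants with imputed data by about 0 to -9 points on bimekizumab and 0 to +5 on placebo, or about 1 point for a whole arm at an assumed 5-15% missing. The tendency is to narrow the treatment difference, so nothing here suggests that the plan favours bimekizumab or that the primary conclusion is unsafe.

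The defects partly offset each other: the raw scale and separate draws lower imputed response, while the shared seed raises it again. Changing only the seed would therefore make the response rate in each arm worse, by about 10 to 20 points among those imputed. The difference between arms need not worsen, as the base scenario shows.

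The hs-CRP loss is roughly 30-50% of the imputed geometric mean at an assumed LLOQ of 0.1-0.2 mg/L, with little bias near 1.0. It affects imputed values of an 'other' endpoint only. That the counts are untransformed is inferred from the SAP's silence and from its -1 example.

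**What to change.** For the lesion counts, adopt these parts together:

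1. Impute abscesses, inflammatory nodules and draining tunnels in one model per arm. Use all three types at earlier visits, and the types already imputed at the same visit, as predictors.
2. In the monotone step use predictive mean matching, or regression on log(1+count) with back-transformation. In the MCMC step for intermittent gaps use log(1+count).
3. Give each run its own documented seed, and reconcile the general seed statement with seeds 853-952 in section 4.2.2.2.

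The same-visit predictors matter. Predictive mean matching on earlier counts alone, with different seeds, stayed about 3-4 points low in both arms; adding the same-visit counts brought it to within 0-3 points of truth. The joint log(1+count) model stayed within about 4 points.

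Separately, impute log(hs-CRP) and back-transform.

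The cost is SAP wording and slightly more programming. The statistical downside is fewer donors for matching in the 70-participant placebo arm.
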